### **3. Concise Summary of Project:**

- The target population for our study is both nulliparous and parous women who present for induction of labor. If there is a decision by the obstetric team to place a transcervical Foley balloon for cervical ripening, the obstetric team will notify the research team so that the patient may be screened for the study. If the subject consents to participation, written informed consent will be obtained by person-to-person contact. The PI or a collaborator will be responsible for the informed consent. After informed consent is obtained, the transcervical Foley balloon will be placed. The method of placement will be left to the discretion of the provider. After placement of the Foley balloon, the subject will be randomized to the study group (early amniotomy) or the control group (delayed amniotomy).

The control group will undergo amniotomy at least four hours after expulsion of the Foley balloon.

The study group will undergo amniotomy as soon as possible after Foley balloon expulsion or within two hours of expulsion.

At any point, if the treating provider determines amniotomy is unsafe, amniotomy may be delayed and performed as soon as the provider deems safe.

This will be an unblinded randomized clinical trial.

No significant adverse effects are expected with the use of amniotomy. The most significant risks associated with amniotomy are fetal heart rate decelerations, ascending infection, umbilical cord prolapse (<1%), rupture of vasa previa (<1%). The subject will undergo inpatient induction of labor, so any adverse reaction would be promptly detected and addressed.

- The number of subjects studied will be 174 subjects at UTMB. The subjects will be withdrawn from the study if she wishes to discontinue participation. If any of the exclusion criteria listed above are met, or there is a change in condition that leads to inclusion

criteria no longer being met, data collection will be terminated and the subject will be withdrawn from the study.

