#### **4.2. Randomization and Masking**

A confidential computer-generated simple randomization scheme (using STATA 16, Dallas, TX) has been prepared. A randomization log with group assignment, subject name, and medical record number will be used to track the randomization process.

Subjects will be randomized in a ratio of 1:1 for delayed or early amniotomy.

Due to the nature of the intervention, blinding of subjects or providers will not be possible.

The subject will be included in the analysis by intent-to-treat once the randomization assignment has been made.

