#### **4.3. Amniotomy**

The control group will undergo delayed amniotomy. At least four hours after Foley balloon expulsion, the provider will perform amniotomy using a plastic amniotomy hook. After amniotomy, standard intrapartum management of the subject will ensue.

The study group will undergo early amniotomy. The provider will perform amniotomy as soon as possible after Foley balloon expulsion or within two hours of expulsion. After amniotomy, standard intrapartum management of the subject will ensue.

If the provider feels the amniotomy is unsafe (floating or ballotable presenting part, head not engaged in the pelvis), amniotomy will be performed as soon as it is deemed safe. If amniotomy is performed outside of the time limits outlined, the subject will remain in the study since we will perform an intent-to-treat analysis.

Foley balloon placement is standard of care in our facility for cervical ripening. Decision for its placement will be solely left to provider's discretion. Both groups will have a foley balloon placed as per standard protocol in our institution.

Oxytocin infusion will be left to provider's discretion based on our unit's standard of practice.

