#### **4.4. Baseline Procedures**

Routine intrapartum care will be provided by the subject's managing obstetric team.

Trained and experienced research staff will be responsible for all research data abstraction.

The PI and collaborators will review and validate the diagnosis for all subjects identified to have the primary outcomes.

Maternal and neonatal outcomes will be assessed following delivery.

Subjects will be encouraged to call the principal investigator with any concerns.

Data collection forms will be used during these processes and charts will be reviewed up to 30 days postpartum. We will collect demographic data, as well as data related to the subject's intrapartum course, delivery, and immediate postpartum period while inpatient. Data on newborn status, including those admitted to the NICU, will be obtained from the infants' charts.

Subjects' participation will end after being discharged home from the hospital.

[figure not shown]

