  - Neonatal infection, defined as sepsis, fever, positive cultures, or a suspicious clinical course that warranted treatment with antibiotics

**5. Sub-Study Procedures:** No sub-studies will be performed

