**9. Potential Risks:**

**9.1. Amniotomy & Randomization Risk**

Since the timing of amniotomy will be randomized, it is possible that the subject may be in a group with higher adverse outcomes, such as early amniotomy. Risks with amniotomy including fetal heart rate decelerations, ascending infection, umbilical cord prolapse, and bleeding due to vasa previa, and it is possible to see a difference in the rates of these complications with earlier amniotomy.

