## **10. Subject Safety, Data Monitoring and Protocol deviations**

Subjects will be continuously monitored throughout their labor course for the development of any adverse events. If a complication is identified, immediate treatment will ensure per standard of care. Study collaborators will be responsible for notifying the principal investigator of any adverse events. The PI and research collaborators will be responsible for monitoring the safety of this study. The PI will notify the faculty sponsor of the occurrence of any adverse events. The yearly report, submitted at time of continuing review, will include participant demographics, expected versus actual recruitment rates, summary of any quality assurance or regulatory issues, summary of adverse events (AEs) or serious adverse events (SAEs) which may have occurred, and any changes in the protocol as a result of these issues.

The PI and collaborators will ensure all aspects of data quality including monitoring for adherence to consent procedures, inclusion and exclusion criteria, valid abstraction, correct entry, timeliness and responsiveness to data queries. The faculty sponsor will be notified by the PI if any issues are identified regarding data quality during the monitoring process.

Data will be collected and stored with the participant ID code only. The master enrollment log linking patient identifiers with study ID numbers will be kept in a password-protected database on the OB/GYN department's internal server separate from the data. Data collection forms will be used. Data on these forms devoid of personal identifiers will be securely stored at our perinatal research division. The PI will be available to monitor the data and correct any discrepancies based on source documents if needed.

For each patient enrolled in the study, their primary obstetric care providers and team currently taking care of the patient will be notified of their participation in person after randomization. For any deviations from study group assignment that may arise, providers will be asked to notify the study team or if missed, the deviation will be identified chart review. The study team will then complete documentation which will be submitted to the IRB as a protocol deviation via InfoEd; according to IRB policies.

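### Neonatal infection pools proven infection with fever and with a decision to give antibiotics, in an open-label trial, so a difference between arms in either direction could reflect prescribing

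*Combined protocol and SAP*

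**What the plan says.** Section 4.10 defines the outcome as "Neonatal infection, defined as sepsis, fever, positive cultures, or a suspicious clinical course that warranted treatment with antibiotics". Any one of the four parts is enough. Sepsis and fever have no stated criterion, and the last part is a clinical judgement combined with a treatment. No rule asks for the parts to be reported separately. Section 2 names neonatal infection among the secondary objectives.

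On knowledge of the arm:
- Section 3: "This will be an unblinded randomized clinical trial".
- Section 4.2: "Due to the nature of the intervention, blinding of subjects or providers will not be possible".
- Section 10, for each enrolled patient: "their primary obstetric care providers and team currently taking care of the patient will be notified of their participation in person after randomization".

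On expectation: section 9.1 lists ascending infection among the risks of amniotomy and adds that "it is possible to see a difference in the rates of these complications with earlier amniotomy".

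On checking: section 4.4 states "The PI and collaborators will review and validate the diagnosis for all subjects identified to have the primary outcomes". For the infants it says only "Data on newborn status, including those admitted to the NICU, will be obtained from the infants' charts". Section 10 adds general checks on abstraction and data entry, but no review of whether a secondary diagnosis represents infection.

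For chorioamnionitis, by contrast, section 4.10 separates a presumptive diagnosis from a confirmed one that needs laboratory or pathological evidence.

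**The concern.** The outcome mixes events that do not depend on who is watching, such as a positive culture, with one that depends on a clinician's threshold to treat. The randomized factor is the timing of membrane rupture, and the protocol itself gives clinicians a reason to think that infection may differ with it. If the threshold to treat varies with knowledge of the arm or of rupture time, the exposure can enter the outcome through prescribing.

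Two misreadings follow. A difference in the pooled rate could be reported as a difference in neonatal infection when only treatment differed. Or similar pooled rates could hide a difference in proven infection. The covariate-adjusted logistic regression in section 13 does not help, because the problem arises after randomization, in how the outcome comes to be recorded. At stake is what the trial can say about neonatal infection, which is one item in a long secondary list.

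**Working it through.** **1. The plan's own figure.** The only sample size in the documents is for time to active phase (section 13): difference 278 min, SD 525 min, two-sided alpha 0.05, power 90%.

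- n per arm = 2 × (1.960 + 1.282)² × 525² / 278² = 74.9, rounded up to 75, so N = 150, as stated.
- 150 / (1 − 0.13) = 172.4, rounded up to 173, against 174 stated, which is close enough.
- At 1:1, 174 / 2 = 87 per arm.

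Nothing here depends on neonatal infection, and no rate for it is given.

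**2. What a pooled difference consists of.** Sort each counted newborn once: (a) proven infection, (b) fever without (a), (c) treated on suspicion without (a) or (b). Then

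pooled difference = difference in (a) + difference in (b) + difference in (c).

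A nonzero total can come from (c) alone, and a total near zero can arise when (a) and (c) differ in opposite directions. The pooled rate cannot tell these cases apart.

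**3. Possible size (illustration; every rate is an assumption).** Let p be the rate that both arms would show under equal prescribing, and x the extra share of otherwise uncounted newborns treated in one arm. That arm's apparent rate is p + (1 − p)x. The last column is the chance of a significant two-sided result at 0.05 with 87 per arm (normal approximation, rough at such small counts).

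| p | x | apparent rate | risk ratio | expected cases | chance significant |
|---|---|---|---|---|---|
| 2% | 2% | 4.0% | 1.98 | 1.7 v 3.4 | 11% |
| 2% | 5% | 6.9% | 3.45 | 1.7 v 6.0 | 35% |
| 2% | 10% | 11.8% | 5.90 | 1.7 v 10.3 | 73% |
| 5% | 2% | 6.9% | 1.38 | 4.4 v 6.0 | 8% |
| 5% | 5% | 9.8% | 1.95 | 4.4 v 8.5 | 22% |
| 5% | 10% | 14.5% | 2.90 | 4.4 v 12.6 | 56% |
| 10% | 2% | 11.8% | 1.18 | 8.7 v 10.3 | 6% |
| 10% | 5% | 14.5% | 1.45 | 8.7 v 12.6 | 15% |
| 10% | 10% | 19.0% | 1.90 | 8.7 v 16.5 | 39% |

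The arms are interchangeable in this table.

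**4. Direction through rupture time.** Section 4.3 says of the early arm: "The provider will perform amniotomy as soon as possible after Foley balloon expulsion or within two hours of expulsion". The control arm's amniotomy comes no sooner than four hours after expulsion, with no upper limit. Assume equal time from placement to expulsion in both arms and the planned 278 min shortening. Then, for time from rupture to 6 cm,

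early minus delayed = (control amniotomy time − early amniotomy time) − 278 min, with both times counted from expulsion.

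- Control at 240 min, early at 0 to 120 min: 240 − 278 = −38, and 120 − 278 = −158. Rupture lasts 38 to 158 min less in the early arm.
- Control at 360 min, early at 0 to 120 min: 360 − 278 = +82, and 240 − 278 = −38. Between 82 min more and 38 min less.

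So the early arm need not have the longer rupture. This stops at 6 cm; the documents give nothing to carry it on to delivery.

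**The case against.** The strongest reply is that bias needs prescribers who know the arm or the rupture time, and the documents never say so. The statement on blinding concerns the amniotomy, and the in-person notice in section 10 goes to the team looking after the enrolled woman. Who treats the newborn, and on what information, is not described. This stands. What remains is that nothing in the plan shields those prescribers either.

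A reader might infer that early amniotomy in particular would look infectious through prescribing alone. The documents do not support that direction: on the plan's own shortening, rupture time could be shorter, similar or longer in the early arm. Knowledge of the arm could still act on prescribing, but its direction is also unstated.

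A reader might also infer that antibiotic-only cases would dominate the pooled rate. No source in the documents says so. Nor does a doubling prove much at this size: 4 of 87 against 9 of 87, itself assumed, gives a risk ratio of 2.25 (95% interval about 0.7 to 7.0; Fisher p = 0.25).

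Finally, if rupture does last longer in one arm, extra antibiotic treatment of newborns is partly a real consequence of the strategy, so the pooled rate is not simply spurious. This is fair. It argues for reporting treatment under its own name, not for leaving it merged with infection. Resting every conclusion on proven infection alone would be debatable, since its events may be very few.

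**Conclusion.** The point holds in a limited form. As defined, the pooled outcome cannot separate neonatal infection from the decision to treat, in a trial with open-label care, a stated expectation that infection may differ, and no diagnostic review of secondary outcomes. A difference in either direction could reflect prescribing, and a difference in proven infection could be masked.

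Size and direction are unknown. The figures of about 6% to 73% for a significant difference rest wholly on assumed rates, with 87 per arm and extra treatment in one arm only. They show what is possible, not what is likely. The primary outcome, its analysis and the sample size are unaffected. This is a worthwhile improvement to a secondary outcome, not a flaw in the main result.

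**What to change.** In section 4.10, keep the pooled outcome and pre-specify that its components are reported separately by arm:

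- (a) proven infection: a positive culture, or sepsis by a stated criterion that does not rest on antibiotic use;
- (b) fever without (a);
- (c) antibiotics for suspected infection without (a) or (b).

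Report rupture-to-delivery time by arm beside these. State that a pooled difference driven by (c) will not be interpreted as a difference in neonatal infection. This extends to the infant the presumptive and confirmed distinction already used for chorioamnionitis.

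The cost is a wording change and a few table lines, since section 4.4 already draws newborn data from the infants' charts. The downside is few events and a wide interval for (a). The change should be made before outcomes are classified, because a split chosen after seeing results would look selective. It alters no clinical care.

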**6. Criteria for Inclusion of Subjects**

- Age  $\geq 18$
- Singleton pregnancy
- Term gestation ( $\geq 37$  weeks gestation)
- Cephalic presentation
- Undergoing labor induction with transcervical Foley balloon

**7. Criteria for Exclusion of Subjects**

- Previous uterine surgery
- Prelabor rupture of membranes
- Severe pre-eclampsia, HELLP, or eclampsia
- HIV, HCV, or HBV
- Heart disease
- Fever ( $\geq 38^{\circ}\text{C}$ ) at admission
- Category II or III fetal heart rate tracing prior to randomization
- Polyhydramnios
- Fetal growth restriction  $<3\%$
- EFW  $> 4200$  g
- Fetal demise or major congenital anomaly
- Prisoners

**8. Sources of Research Material:** Electronic medical chart / records

**9. Potential Risks:**

**9.1. Amniotomy & Randomization Risk**

Since the timing of amniotomy will be randomized, it is possible that the subject may be in a group with higher adverse outcomes, such as early amniotomy. Risks with amniotomy including fetal heart rate decelerations, ascending infection, umbilical cord prolapse, and bleeding due to vasa previa, and it is possible to see a difference in the rates of these complications with earlier amniotomy.

## **9.2. Loss of Confidentiality**

Any time information is collected, there is a potential risk for loss of confidentiality. Every effort will be made to keep subject's information confidential; however, this cannot be guaranteed.

## **10. Subject Safety, Data Monitoring and Protocol deviations**

Subjects will be continuously monitored throughout their labor course for the development of any adverse events. If a complication is identified, immediate treatment will ensure per standard of care. Study collaborators will be responsible for notifying the principal investigator of any adverse events. The PI and research collaborators will be responsible for monitoring the safety of this study. The PI will notify the faculty sponsor of the occurrence of any adverse events. The yearly report, submitted at time of continuing review, will include participant demographics, expected versus actual recruitment rates, summary of any quality assurance or regulatory issues, summary of adverse events (AEs) or serious adverse events (SAEs) which may have occurred, and any changes in the protocol as a result of these issues.

The PI and collaborators will ensure all aspects of data quality including monitoring for adherence to consent procedures, inclusion and exclusion criteria, valid abstraction, correct entry, timeliness and responsiveness to data queries. The faculty sponsor will be notified by the PI if any issues are identified regarding data quality during the monitoring process.

Data will be collected and stored with the participant ID code only. The master enrollment log linking patient identifiers with study ID numbers will be kept in a password-protected database on the OB/GYN department's internal server separate from the data. Data collection forms will be used. Data on these forms devoid of personal identifiers will be securely stored at our perinatal research division. The PI will be available to monitor the data and correct any discrepancies based on source documents if needed.

For each patient enrolled in the study, their primary obstetric care providers and team currently taking care of the patient will be notified of their participation in person after randomization. For any deviations from study group assignment that may arise, providers will be asked to notify the study team or if missed, the deviation will be identified chart review. The study team will then complete documentation which will be submitted to the IRB as a protocol deviation via InfoEd; according to IRB policies.

## **11. Procedures to Maintain Confidentiality**

- The data collected will be indirectly linked to the subject by subject's MRN number.
- When the subject accepts to participate in the study, a number will be attributed to the subject, and this number will be entered on the data collection sheet.

- The data collected will be transferred to the PI's password-secured UTMB computer that is stored in a locked room using an USB flash drive.
- The study PI will be the only person to have a list with the number designated to each subject and the corresponding subject's MRN number. This list will be kept in a locked cabinet of the PI's locked UTMB office. This identifier is needed to access and analyze demographic data. During analysis of the data, all identifiers will be deleted.
- Data will not be disclosed to outside persons or entities.

## 12. Potential Benefits

Subjects who undergo either early or delayed amniotomy may be at decreased risk for adverse perinatal outcomes. If this is the case, our study stands to benefit women who have amniotomy in future cases of labor induction.

## 13. Statistical Approach

Analysis will be performed by intent to treat. Univariable and multivariable analysis will be used to describe the population in the study and to identify potential confounding variable. For this analysis normality will be tested using Shapiro-Wilk method. Demographics and descriptive statistics such as t test, Pearson's chi square, and Mann-Whitney tests will be used as indicated. Data will be either shown as median +/- Range or mean +/- SDEV. Statistical analyses of primary and secondary outcomes between two groups will be performed by multivariate logistic regression analysis accounting for confounding variables if indicated.

Based on our prior results (DILAFOL Trial), women who received Foley balloon and delayed amniotomy reached active phase of labor in 1111 mins with a standard deviation of 525 mins. Using difference rate of 25%, power of 90% and 2-sided alpha of 0.05, we estimate that we will need 150 with complete ascertainment. This difference of 278 or ~4hours was decided after consulting clinical experts in the field of obstetrics, supporting clinical reasoning that a difference between both methods is clinically significant. Detailed from stata 16 : Estimated sample sizes for a two-sample means test (z test) ;Study parameters: alpha = 0.0500; power = 0.9000; delta = -278.0000; mean1 = 1111.0000; mean2 = 833.0000 sd = 525.0000 Estimated sample sizes: N = 150

N per group = 75. Assuming a 13% loss to follow, we propose to enroll a total of 174 subjects. Analyses will be performed by intent to treat. We will be using STATA 16 (Dallas, TX) for statistical computations

This trial will be registered with Clinical Trials Register (Clinicaltrials.gov), before recruitment is initiated and after IRB approval.

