#### **4.6. Withdrawals**

Subjects who withdraw from the study after randomization will be excluded from further follow-up. Outcomes ascertained up until the time of withdrawal will be reported in intent-to-treat fashion.

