## Study Summary Flow Diagram

#### 4.9. Primary Outcomes

- Time interval from Foley balloon placement to reaching the active phase of labor (6 cm cervical dilation)

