#### 4.10 Secondary Outcomes

- Induction to delivery time in minutes
- Time interval from completion of cervical ripening to delivery in minutes
- Vaginal delivery within 24, 36 and 48 hours of induction
- Cesarean section rates and indications
- Operative delivery rates
- Total length of hospital stay
- Maternal outcomes
  - Isolated maternal fever
  - Chorioamnionitis (also known as “IAI,” or “triple I”):
    - A **presumptive diagnosis** of IAI (suspected triple I) can be made in women with:
      - **Fever** –  $\geq 39.0^{\circ}\text{C}$  [ $102.2^{\circ}\text{F}$ ] **or**  $38.0^{\circ}\text{C}$  [ $100.4^{\circ}\text{F}$ ] to  $38.9^{\circ}\text{C}$  [ $102.02^{\circ}\text{F}$ ] on two occasions 30 minutes apart, without another clear source **PLUS** one or more of the following [1]:
        - Baseline fetal heart rate  $>160$  beats/min for  $\geq 10$  minutes, excluding accelerations, decelerations, and periods of marked variability
        - Maternal white cell count  $>15,000/\text{mm}^3$  in the absence of corticosteroids and ideally showing a left shift (bandemia)
        - Purulent-appearing fluid coming from the cervical os visualized by speculum examination
      - A **confirmed diagnosis** of IAI can be made in women with:
        - **All of the above** **PLUS** one or more of the following objective laboratory findings:
          - Positive Gram stain of amniotic fluid
          - Low glucose level in amniotic fluid
          - Positive amniotic fluid culture
          - High white cell (WBC) count in amniotic fluid in the absence of a bloody tap
          - Histopathologic evidence of infection or inflammation or both in the placenta, fetal membranes, or the umbilical cord vessels (funisitis)
        - Endometritis - must meet the following criteria:
          - Infection occurs within 30 days after the operative procedure AND
          - Infection presumed to involve the uterus AND
          - Subject has at least one of the following:

- Purulent drainage from a drain that is placed through a stab wound into the abdomen or pelvis
- Organisms isolated from an aseptically-obtained culture of fluid or tissue in the organ / space
- Postpartum hemorrhage
  - EBL >1000 cc
- Wound infection
- Umbilical cord prolapse
- Neonatal outcomes
  - Apgar score <7 at 1 and 5 minutes
  - Cord arterial pH <7.0
  - NICU admission

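### Section 13 assigns a primary outcome measured in minutes to logistic regression, with covariates chosen from the trial data, so no usable primary model is fixed in advance

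*Combined protocol and SAP*

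**What the plan says.** All of the analysis text is in Section 13.

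- On covariates: "Univariable and multivariable analysis will be used to describe the population in the study and to identify potential confounding variable". Normality is to be tested by Shapiro-Wilk for that work.
- On simple tests: "Demographics and descriptive statistics such as t test, Pearson's chi square, and Mann-Whitney tests will be used as indicated".
- On the outcomes: "Statistical analyses of primary and secondary outcomes between two groups will be performed by multivariate logistic regression analysis accounting for confounding variables if indicated".
- On sample size: an unadjusted two-sample means z test, 1111 against 833 min, SD 525 min, two-sided alpha 0.05 and 90% power. It gives 75 per arm and 150 in total, raised to 174 for 13% loss.

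Section 4.9 defines the primary outcome as "Time interval from Foley balloon placement to reaching the active phase of labor (6 cm cervical dilation"), an interval with no threshold attached. Section 3 enrolls both nulliparous and parous women. Section 4.2 describes the allocation: "A confidential computer-generated simple randomization scheme (using STATA 16, Dallas, TX) has been prepared". No stratification factor is named. The same section rules out blinding of subjects and providers, and sets the analysis population: "The subject will be included in the analysis by intent-to-treat once the randomization assignment has been made".

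No section lists a covariate, gives a rule for choosing one, says when adjustment is indicated, or says whether the adjusted or the unadjusted result is primary.

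**The concern.** Three parts of the plan point to three different analyses. The outcome is a continuous time, the model assigned to it is for a binary response, and the sample size comes from an unadjusted difference in means. An analyst following Section 13 literally could not run the primary analysis without making a choice that the plan does not make.

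Two things are at stake. If the logistic instruction is obeyed, the time must be cut into a yes/no outcome, which discards information that the sample size relied on. If it is not obeyed, the model and its covariates are picked once data are available. Arms are known to patients and providers, and no blinded analyst is described, so a model written down beforehand is the main protection against a result-driven choice.

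A search for confounders also has little role in a randomized comparison. Randomization removes confounding in expectation, and the useful reason to adjust is precision. For that, covariates should be baseline variables named in advance. Parity is the obvious candidate, since both parity groups are enrolled, yet it is nowhere fixed as a covariate.

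**Working it through.** **1. The plan's own figure (inputs from Section 13).**

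n per arm = 2 × 525² × (1.960 + 1.282)² / 278² = 74.95, so 75 per arm and N = 150. Loss: 150 / 0.87 = 172.4, so 173, or 174 with equal arms. Both figures reproduce.

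SE of the difference = 525 × √(2/75) = 85.7 min. Power = Φ(278/85.7 − 1.96) = Φ(1.283) = 0.900. The 95% CI half-width is 1.96 × 85.7 = 168 min.

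**2. Cost of obeying the logistic instruction.** The plan gives no cut-point, so the cuts below are assumptions, as is normality of the times. For cut c, the proportions reaching 6 cm by c are p1 = Φ((c − 1111)/525) for delayed and p2 = Φ((c − 833)/525) for early amniotomy. With n = 75 per arm, d = p2 − p1 and p̄ the mean of the two,

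power = Φ{[d√n − 1.96√(2p̄(1 − p̄))] / √(p1(1 − p1) + p2(1 − p2))}.

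| Cut (min) | p1 | p2 | Power, 75 per arm | N for 90% power |
|---|---|---|---|---|
| 833 | 0.298 | 0.500 | 0.718 | 244 |
| 972 | 0.396 | 0.604 | 0.729 | 238 |
| 1111 | 0.500 | 0.702 | 0.718 | 244 |
| 1440 | 0.735 | 0.876 | 0.593 | 326 |

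For example, at 833 min: (0.2018 × 8.660 − 1.96 × 0.6926) / 0.6777 = 0.576, and Φ(0.576) = 0.718.

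**3. Cost of an open choice of model.** Null simulation, 20,000 trials of N = 150. Assumptions not in the documents: 50% nulliparous, and a parity shift in time to 6 cm of 200, 300 or 400 min.

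| Analysis, normal times | 200 min | 300 min | 400 min |
|---|---|---|---|
| Unadjusted only | 5.0% | 4.7% | 5.1% |
| Parity-adjusted only | 5.0% | 4.8% | 5.0% |
| Better of the two reported | 5.9% | 6.1% | 6.8% |

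With skewed times (gamma residuals, shape 4), the better of the two gives 5.9%, 6.4% and 6.7%. Covariate-selection rules applied mechanically give 4.7-5.3%. At a true 278 min effect, the two tests disagree on significance in about 3-6% of trials.

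**4. What a fixed parity-adjusted linear model would give.** With nulliparous share p = 0.5 and shift D, R² = p(1 − p)D²/525², and the adjusted SE is 85.7 × √(1 − R²).

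| D (min) | R² | SE (min) | Power | 95% CI half-width (min) |
|---|---|---|---|---|
| 200 | 0.036 | 84.2 | 0.910 | 165 |
| 300 | 0.082 | 82.2 | 0.923 | 161 |
| 400 | 0.145 | 79.3 | 0.939 | 155 |

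With 30% or 70% nulliparous, power is 0.909, 0.919 and 0.933.

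**The case against.** The best defense is that the harm is largely hypothetical. The unadjusted comparison of means is valid and has its 90% power. Type I error rises only if someone fits both models and reports the better one, which Section 13 does not say will happen. Choosing between t test and Mann-Whitney by the Shapiro-Wilk check, simulated under the null with 8,000 trials per setting, kept type I error at 4.7-5.0%. Parity's share and effect are not in the documents, and the gain from adjusting for it is only 1 to 4 points of power.

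Most of this stands, and it limits the size of the point. It does not remove it. The means test appears in Section 13 only as the basis of the sample size, and the t test and Mann-Whitney test are listed as descriptive. The one method assigned to the primary outcome is logistic regression. Intent to treat settles who is analyzed, not by which model.

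Several stronger readings are tempting and are not supported:

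- A reader might infer that the trial is underpowered. It is not: N = 150 is right for the test used to derive it. The 59-73% applies only if the time is dichotomized, which the plan does not say it will do.
- A reader might infer that the plan as written has a 6-7% error rate. That is a worst case, not a property of the stated rule.
- A reader might infer that simple randomization without stratification biases the result through parity imbalance. Chance imbalance is already reflected in the unadjusted SE and is not an error in the plan.
- A reader might infer that this point also decides how to treat women delivered by cesarean before 6 cm. It does not. Section 4.10 lists "Cesarean section rates and indications" as an outcome, and Section 4.6 says "Outcomes ascertained up until the time of withdrawal will be reported in intent-to-treat fashion", but which estimand applies to those women is a separate question.

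**Conclusion.** The point holds. Section 13 names a model that cannot be fitted to the primary outcome as defined and that differs from the test behind the sample size. It leaves covariates and the trigger for adjustment to the trial data. This is a stated rule that would serve the trial badly, not merely a missing detail.

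The larger cost would come from following the logistic instruction, about 17 to 31 points of power (90% down to 59-73%) at the assumed cuts. The cost of the open choice is smaller: at worst 1 to 2 points of type I error under the assumed parity figures, and about none under a fixed rule. Neither invalidates the trial. The text should be corrected before outcomes are analyzed.

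**What to change.** Replace the confounder-search sentence and the logistic regression sentence in Section 13 with:

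> The single primary analysis is a linear regression of time from Foley placement to 6 cm (minutes) on treatment arm and parity (nulliparous vs parous), by intent to treat. Only this baseline covariate is used; none is added or dropped on trial data. The unadjusted comparison of means is a sensitivity analysis. Continuous secondary outcomes use the same linear model; logistic regression on arm and parity is used only for binary secondary outcomes.

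This keeps the difference in minutes on which the sample size was built and needs no additional patients. Parity can be taken from the medical record, the data source in Section 8. The cost is a change of wording, one degree of freedom, and the move of the unadjusted result to second place. If the sponsor prefers the unadjusted means comparison as primary, that would also close the gap, provided it is named as the only primary analysis and any adjustment is stated in advance. The handling of cesarean before 6 cm should be specified separately.
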